All arms: 
• To evaluate the changes from baseline in the biomarkers of tumor biology and anti-tumor activity	All arms: 
• The biomarker endpoints will be:
▪ Genomic molecular profile (NGS by MSK-IMPACT) on the fresh tumor biopsy of metastatic tumor▪ RNA sequencing on the fresh tumor biopsy of metastatic tumor▪ Cell-free DNA in serial plasma samples (NGS by MSK-ACCESS)▪ pMEK and pERK changes in the cytoplasm and nucleus

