3.0 BACKGROUND AND RATIONALE

3.1 Mirdametinib

Mirdametinib is a highly selective and potent, non-ATP-competitive oral inhibitor of MEK1 and MEK2 kinases. It significantly inhibits the phosphorylation of the MAP kinases ERK1 and ERK2, leading to impaired tumor cell growth in vitro and in vivo with an IC50 of approximately 0.3 nM based on in vitro cellular assays and PK/PD of mouse xenograft

Memorial Sloan Kettering Cancer Center
[name]
[name]

tumor models. Mirdametinib has exhibited anti-tumor activity against a broad spectrum of human tumors in cell lines and animal xenograft models.

The plasma PK profile of mirdametinib is characterized by rapid absorption with the Cmax achieved by approximately 1-hour post-dose and bi-phasic elimination with a terminal elimination half-life ranging from 22 to 30 hours. Mirdametinib (PD-0325901) is largely eliminated by conversion to a primary active metabolite (PD-0315209) which has a half-life ranging from 30 to 40 hours. Generally, exposure of mirdametinib (both Cmax and AU_{tau}) increases proportionally with increases in dose from 1 to 30 mg QD or BID. Mirdametinib exposure following multiple doses exhibited a small degree of accumulation exhibiting accumulation ratios for AU_{tau} ranging from 1.3 to 1.9 after 21 days of BID dosing. Accumulation of the primary metabolite, PD-0315209, was higher at approximately 3-fold.

Mirdametinib is a substrate of CYP3A4, CYP1A2, CYP2C9 and CYP2C19, however, conversion of mirdametinib to the primary metabolite PD-0315209 is largely mediated by non-CYP enzymes. Therefore, inhibition of CYP enzymes is unlikely to significantly alter the pharmacokinetics of mirdametinib. Mirdametinib is a substrate of both P-gp and BCRP. Inhibition of P-gp may increase the absorption of mirdametinib. However, in the absence of P-gp inhibitors, mirdametinib is extensively and rapidly absorbed due to its high permeability and solubility. Only small amounts of mirdametinib are eliminated in urine and feces unchanged. Therefore, inhibition of P-gp is not likely to have a significant impact on the systemic exposure of mirdametinib. Mirdametinib is not a significant inhibitor of CYP enzymes or major drug transporters with the exception of OAT1 which may be inhibited at clinically relevant concentrations.

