4.2 Intervention

Study Periods

Each subject will undergo 3 periods (screening, treatment, and post-study follow-up).

Screening

The screening period will be from the signing of the informed consent until the first dose of the first study drug on Day 1 of Cycle 1 (C1D1). The screening period should not exceed 28 calendar days before C1D1.

Treatment

A treatment cycle lasts 28 days. The treatment period will be from the first dose of the first study drug until the last dose of the last study drug.

The treatment will continue until the disease progression, death, unacceptable toxicity, withdrawal of consent, or another reason for permanent discontinuation of treatment.

Patients with documented progression of disease may be allowed to continue on study if the patient is tolerating treatment, and in the opinion of the investigator, the patient is deriving clinical benefit from continuing study treatment and continuation of treatment is approved by the principal investigator. If said patient continues treatment post progression, they will require reconsent.

Dose levels of mirdametinib are summarized in section 10.2.

Post-study Follow-up

The post-study follow-up will include the end of treatment (EoT) visit, the safety follow-up visit, and the long-term follow-up.

An End of Treatment (EoT) visit will be performed within 7-14 days after the administration of the last dose of the last study drug.

The safety follow-up (FU) visit will be performed 30 days after the last dose of the last study drug treatment (except for subjects who died, withdrew consent, and objected to further data collection or were lost to follow up). The safety FU assessment can be done via the clinic visit (recommended) or via a phone call (if subject cannot attend the clinic visit or has started a new anti-cancer treatment). The investigator may order unscheduled FU visits after the 30-day safety FU visit if the adverse events ongoing at the safety FU are deemed to be clinically significant and related to the study drug(s).

The long-term follow-up will aim to obtain the information necessary for the duration of response (DOR) and the progression-free survival (PFS) endpoints. The long-term follow-up visits will be performed via clinic visit or phone call about every 3 months for 12 months

Memorial Sloan Kettering Cancer Center
[name]
[name]

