 - b. If 1 of the first 3 evaluable subjects in Dose Level -2INT exhibit a DLT in Cycle 1, then a sufficient number of subjects will be treated with mirdametinib 2 mg BID PO, intermittently dosed, in combination with the recommended dose of fulvestrant to accrue 6 evaluable subjects.
 - c. If ≤ 1 of 6 evaluable subjects in Dose Level -2INT exhibit a DLT in Cycle 1, then **mirdametinib 2 mg BID PO**, intermittently dosed, will be declared as the recommended dose for Part 2 (RP2D) in combination with fulvestrant.
 - d. If ≥ 2 of the first 3 evaluable subjects or ≥ 2 of the 6 evaluable subjects in Dose Level -2 exhibit a DLT in Cycle 1, then the Arm 1 will be discontinued. The reason for discontinuation of Arm 1 will be that 2 mg BID PO, dosed intermittently, is deemed to be the minimum dose required for sufficient clinical benefit from mirdametinib in combination with fulvestrant in the refractory metastatic breast cancer.

Arm 1 - Part 2 (Expansion Cohorts)

The following expansion treatment groups (up to 28 subjects each). Both cohorts are planned and the rationale for sample size is included in section 14.5. These will initially be started, either in parallel or sequentially depending on the results of Part 1:

Memorial Sloan Kettering Cancer Center
[name]
[name]

1. Subjects with hormone receptor-positive, HER2-negative metastatic breast cancer exhibiting NF1 loss defined as homozygous deletion of NF1 by NGS assay; truncating or nonsense mutations in NF1; OncoKB defined pathogenic missense mutation; OncoKB defined activating mutation in KRAS or HRAS.
2. Subjects with hormone receptor-positive, HER2-negative metastatic breast cancer exhibiting EGFR amplification defined as >1.9 copies of EGFR by NGS assay; ERBB2 hotspot somatic mutation defined as activating by OncoKB.

The above expansion treatment groups are prioritized for this study, however as an exploratory treatment group to be considered in the future is the following cohort:

1. Subjects with hormone receptor-positive, HER2-negative metastatic breast cancer exhibiting OncoKB defined activating mutations in BRAF, CRAF, or MEK1/2

Arm 2 – Part 1 (Dose escalation of mirdametinib as single agent)

Part 1 will be conducted in three sequential Dose Level escalations according to the 3+3 design based on the incidence of dose-limiting toxicities (DLT) and the overall safety profile of the study treatments. The DLT definitions are listed in [Section 15.3](#).

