10.1 Mirdametinib Study Treatment

- Subjects will be instructed to take mirdametinib at home and record the time of intake for both daily doses in the patient dosing diary. Missed doses will also be recorded in the dosing diary. Subjects will be instructed to **not** take their planned morning dose of mirdametinib prior to each study visit during the treatment period. Instead, the morning dose will be taken following the pre-dose PK blood draw or any other assessment scheduled to be obtained at pre-dose during the visit.
- Mirdametinib treatment will be dispensed to subjects every two Cycles during scheduled study visits as described in the SoA or at an unscheduled visit if mirdametinib treatment is damaged/lost.
- Throughout the treatment period, subjects will self-administer study treatment BID utilizing a continuous dosing schedule in 28-day Cycles.
- Subjects will be instructed to swallow capsules whole and not to open or chew them prior to swallowing.
- No capsule should be ingested if it is broken, cracked, or otherwise not intact.
- Subjects should be encouraged to take their dose approximately every 12 hours
- Subjects can take mirdametinib capsules without regard to food intake.
- Delivery of mirdametinib via nasogastric tube or gastrostomy tube is not allowed.
- If a subject misses a scheduled dose of study treatment, and it is within 6 hours of the scheduled dose, the subject should immediately administer the missed dose and resume study treatment in accordance with the normal administration schedule. If more than 6 hours has elapsed since the time of scheduled administration, the subject will **not** be instructed to administer the missed dose and to resume study treatment as prescribed.
- Subjects should not take 2 doses together to “make-up” for a missed dose.
- If a subject vomits any time after taking a dose, then they must be instructed not to take another dose to “make up” for vomiting, but rather, to resume subsequent doses as prescribed.

Memorial Sloan Kettering Cancer Center
[name]
[name]

- If a subject inadvertently takes 1 extra dose, then the subject should not take the next scheduled dose of study treatment. Only one dose should be skipped in this context.

The dose levels for mirdametinib are summarized as follows:

Dose Level -2INT	2mg PO BID, 3 weeks on/1 week off
Dose Level -2	2mg PO BID given continuously
Dose Level -1INT	3mg PO BID, 3 weeks on/1 week off

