Total cholesterol, LDL, Triglycerides ¹⁵	X	X		X		X			

Memorial Sloan Kettering Cancer Center
 [name]
 [name]

Coagulation (aPTT and PT or INR) ¹⁵	X	X		X		Cycle 5 and every odd Cycle thereafter	X	X	
Thyroid function (TSH, FT3, FT4) ¹⁵	X	X		X		Cycle 5 and every odd Cycle thereafter	X	X	
Virology ²	X								
Pregnancy test (only WOCBP) ⁴	X		X			X	X		
Mirdametinib dosing ⁵		Twice daily (Morning dose will be taken in the clinic on Cycle 1 Days 1 and 15, and Cycle 2 Day 1)							
Fulvestrant IM injection		X	X	X		X			
PK sampling for mirdametinib ⁶		X	X	X					
Ophthalmological examination ⁷	X					Cycle 3 and every odd Cycle thereafter (+/- 7 days)	X		
Echocardiogram ⁸	X					Cycle 3 and every odd Cycle thereafter (+/- 7 days)	X		
Tumor assessment by RECIST 1.1 ⁹	X					C3, then every 8 weeks (+/- 5 days) until cycle 11, then every 12 weeks (+/- 7 days) on cycles 12 and above	X		
On-Treatment Tumor biopsy – Core Needle (Optional) ¹⁰				Within 7 days of C2D1					
Tumor markers		X		X		Day 1 of every cycle until the first scan, and then coinciding with imaging time points	X		
MSK-Access cfDNA		X					X		
cfDNA collection				X		X			

1. Vital signs should include body temperature, height (required at screening, only) and weight, blood pressure, heart rate, and pulse oximetry.
2. Virology at screening will include the following assessments:
 - HBV: HBsAg and HBV-DNA
 - HCV: anti-HCV antibody and HCV-DNA
3. Archival tumor: Sufficient if within 6 months of trial enrollment. If archival tissue is not available a core needle biopsy is mandatory, as long as the investigator deems the procedure to be safe and accessible. A sample of the archival tumor tissue from the primary or metastatic tumor (block preferred, or at least 5 FFPE slides) will be

Memorial Sloan Kettering Cancer Center
 [name]
 [name]

collected at screening.

4. **Pregnancy test:** women of childbearing potential must have a negative serum pregnancy test within 3 days before dosing on Day 1 in each cycle
5. **Study drug administration:**
 - a. Mirdametinib dosing at home: twice daily by mouth on every day of each 28-day cycle except for the morning dose on Day 1 and Day 15 in each cycle.
 - b. Mirdametinib dosing in the clinic: the clinic staff will administer the morning dose of mirdametinib on Cycle 1 Days 1 and 15 and Cycle 2 Day 1.
6. **PK sampling:** Blood samples for mirdametinib concentration in plasma will be drawn at the following time points:

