 - a. Day 1 and Day 15 of Cycle 1: pre-dose and at 0.5h, 1.0h, 2.0h and 4.0h after the mirdametinib dose
 - b. Day 1 of Cycle 2: pre-dose
7. **Ophthalmological exam:** must include visual acuity, tonometry, slit lamp exam and optical coherence tomography (OCT); fundoscopy with pupil dilation is not mandatory but may be performed at the discretion of the ophthalmologist. For cycles that do not have a scheduled ophthalmological exam, the treating physician will evaluate the participant for ocular toxicity and refer them to an ophthalmologist if clinically indicated.
8. **LVEF assessment by echocardiogram (Echo),** where the exam may be limited only on the measurement of LVEF without other aspects (global and regional contractility, stroke volume etc.), unless requested at the investigator's discretion. Results from a MUGA scan can also be used if it is performed as part of the patient's routine care.
9. **Imaging** to be performed within five-day window up to cycle 12, then within 7-day window for cycles 12 and above
10. **Paired tumor on-treatment biopsy – Core Biopsy (Optional).** If tumor lesion is accessible at acceptable risk and the patient has consented, the core biopsy will be obtained from the primary or metastatic tumor within 7 days before C2D1.
11. Clinical/local lab tests are listed in Table 2
12. The triplicate ECG will be done pre-dose and at 4 hours post-dose on C1D1 and C2D1. All other triplicate ECGs will be obtained pre-dose.
13. The long-term follow-up visits may be done in clinic or via telehealth
14. Baseline characteristics of these patients will utilize laboratory and clinical studies performed on C1D1.
15. Laboratory Assessments and Urinalysis: must be completed within 3 days before dosing on Day 1 of each cycle except for on Cycle 1 Day 1 (which must be completed on same day)

Memorial Sloan Kettering Cancer Center
[name]
[name]

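### On the 3-weeks-on/1-week-off dose levels, the single window for the optional on-treatment biopsy coincides with the week without mirdametinib

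*Combined protocol and SAP*

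**What the plan says.** Section 4.2 fixes the cycle length: "A treatment cycle lasts 28 days". The dose-level list in Section 10.1 has two intermittent levels: -2INT for Arm 1, "2mg PO BID, 3 weeks on/1 week off", and -1INT for Arm 2, "3mg PO BID, 3 weeks on/1 week off". Either can become the dose for the expansion cohorts. For Arm 1, Section 4.2 step 4c says that 2 mg BID, "intermittently dosed, will be declared as the recommended dose for Part 2 (RP2D"); step 4c for Arm 2 is the parallel rule for 3 mg BID.

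The biopsy timing is in Table 3 (Schedule of Assessments). Footnote 10 says "the core biopsy will be obtained from the primary or metastatic tumor within 7 days before C2D1". The Table 3 cell says "Within 7 days of C2D1" and names no side of that visit; Appendix III is equally loose. None of these places distinguishes continuous from intermittent levels.

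The paired samples serve the exploratory objective in Section 2.0, change from baseline in biomarkers. Its endpoints include "pMEK and pERK changes in the cytoplasm and nucleus" and RNA sequencing of fresh biopsies. Appendix I assigns frozen cores to RNA and protein work. Sections 11.9.2.1 and 11.9.2.2 make the on-treatment biopsy optional.

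**The concern.** A pharmacodynamic biopsy is meant to show what the drug does to the pathway while it is being given. Footnote 10 does this on continuous dosing. On an intermittent level, the last seven days of the cycle are the days without mirdametinib. The sample would still be called on-treatment and paired with the screening biopsy, and it could be pooled with samples from patients dosed within the previous 12 hours or so.

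At stake is the interpretation of an invasive research sample. A small change in pMEK or pERK could mean weak inhibition or simply a late biopsy day. Table 3 seems to have been written for continuous dosing: footnote 5a and Section 10.1 both describe mirdametinib on every day of the cycle.

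**Working it through.** **Inputs**
- Cycle length 28 days (Section 4.2), so C2D1 is nominal Day 29.
- Biopsy window: the 7 days before C2D1 (Table 3, footnote 10).
- Intermittent dosing: 3 weeks on, 1 week off (Section 10.1). The documents do not number the days; Days 1-21 on and Days 22-28 off is the plain reading and is assumed here.
- Parent drug: "terminal elimination half-life ranging from 22 to 30 hours" (Section 3.1). Active metabolite half-life: 30-40 h (same section).
- Last dose assumed on the evening of Day 21.

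**Step 1: calendar.** Window = Day (29 - 7) to Day (29 - 1) = Days 22-28. Overlap with dosing Days 1-21 is 0 of 7 days; overlap with the off week is 7 of 7.

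**Step 2: sensitivity to the visit window and the looser wording.** Table 3 allows ±3 days for treatment visits.
- C2D1 three days early: window is Days 19-25, of which 3 (Days 19-21) are dosing days.
- C2D1 three days late: window is Days 25-31, with no dosing days if dosing restarts at the visit.
- Table 3 cell read as either side of C2D1: window is Days 22-36, of which 7 are off days and 8 run from C2D1 onward.

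On the nominal calendar, even the loosest reading still contains the whole off week.

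**Step 3: drug remaining.** Fraction remaining = 0.5^(t / half-life), relative to the level at the last dose.

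| Time since last dose | Nominal day | Parent (22-30 h) | Active metabolite (30-40 h) |
|---|---|---|---|
| 12 h | 22, morning | 68.5-75.8% | 75.8-81.2% |
| 24 h | 22, evening | 46.9-57.4% | 57.4-66.0% |
| 84 h | 25, morning | 7.1-14.4% | 14.4-23.3% |
| 168 h | 28, evening | 0.5-2.1% | 2.1-5.4% |

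The fall from 24 h to 168 h spans 144 h:
- Parent: 2^(144/30) = 28-fold to 2^(144/22) = 93-fold.
- Metabolite: 2^(144/40) = 12-fold to 2^(144/30) = 28-fold.

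This uses terminal half-lives only. It ignores the faster first phase for the parent and continued formation of metabolite from the parent, so the figures show the spread and are not predicted concentrations.

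**Step 4: contrast with continuous levels.** With doses about 12 hours apart, a patient on a continuous level biopsied on Days 22-28 stays near the first row of the table or above it. A patient on an intermittent level may be anywhere in the table, depending on when the biopsy is scheduled.

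**The case against.** The calendar overlap is hard to dispute. The case against concerns its reach and consequence, and much of it stands.

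- **Reach.** A reader might infer that a whole expansion of 56 evaluable patients (goal enrolment 60, Section 14.5) would have misplaced biopsies. The documents do not support that. Those are enrolment figures; paired biopsies are optional and meant for a subset with accessible tumors, and no number of biopsies is stated.
- **Likelihood.** In Arm 1 the intermittent level opens only after 4 mg and 2 mg continuous both fail. In Arm 2 it opens only after 4 mg and 3 mg continuous both fail, and at the investigator's discretion. As a rough illustration, take the rounded pass probabilities in the Section 14.1 table and assume the same DLT risk at all three levels. Fail × fail × pass is then 0.1 × 0.1 × 0.9 = 1% at a true risk of 0.1, 0.3 × 0.3 × 0.7 = 6% at 0.2, 0.5 × 0.5 × 0.5 = 12.5% at 0.3, and 0.7 × 0.7 × 0.3 = 15% at 0.4. Equal risk is an assumption, and the Arm 1 rules differ slightly.
- **Off treatment altogether.** That is too strong for Arm 1. Fulvestrant is given on Days 1 and 15 of Cycle 1 (Section 5.2), so the patient is off mirdametinib only, and RNA changes would still reflect fulvestrant.
- **Pathway recovery.** A reader might infer that the biopsy would show restored signaling and be read as failure to inhibit MEK. The documents give no plasma concentrations at these doses and no pERK recovery kinetics. About half the parent remains at 24 h, so an early-window biopsy is not drug-free.
- **Recoverable timing.** Section 10.1 has patients record the time of each dose in a diary, so time since last dose can be reconstructed and analyzed. This softens the problem but does not put the biopsy on a dosing day.

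What remains is a stated window that, at two dose levels, misses every nominal mirdametinib dosing day, with nothing in the documents saying that this is intended.

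**Conclusion.** The point holds as a minor design correction. On Dose Levels -2INT and -1INT the footnote 10 window overlaps 0 of 7 nominal mirdametinib dosing days. Exposure within it falls 28- to 93-fold for parent drug and 12- to 28-fold for the active metabolite between 24 h and 168 h. The exploratory pMEK/pERK and RNA changes would be taken at uncontrolled, declining mirdametinib exposure and could not be compared directly with biopsies from continuous levels. How far the pathway would recover cannot be computed from the documents.

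The conclusion rests on dosing on Days 1-21, an on-time C2D1, and footnote 10 governing over the looser Table 3 and Appendix III wording. It has consequences only if an intermittent level is opened or becomes the RP2D, and only for the unstated number of patients who agree to the biopsy. Primary safety and efficacy analyses are unaffected.

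**What to change.** In footnote 10 and the Table 3 row, state that on 3-weeks-on/1-week-off levels the optional on-treatment biopsy is taken in the last mirdametinib dosing week of Cycle 1 (Days 15-21). Leave the window for continuous levels as it is. Capture time since last dose with each sample, using the dosing diary, and use it in the analysis of biomarker change. Reconcile the Table 3 cell and Appendix III with footnote 10 so that all three name the same side of C2D1.

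If an off-week biopsy is in fact intended, say so and analyze those samples separately.

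The cost is a sentence or two and one added data item, with no extra biopsy and no change to dosing. The small downside is that the biopsy comes about a week earlier than on continuous levels, so time on study differs between the two sets of samples.

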11.4 Electrocardiograms (ECGs)

To evaluate the QT/QTc interval in patients treated with mirdametinib, either with or without fulvestrant, will be monitored with a standard 12-lead ECG performed in triplicate (≥ 1 minute apart) at different timepoints. Patients should be in supine position and resting for at least 10 minutes before study-related ECGs. ECG monitoring should be performed prior to PK blood draws. Details can be found in the Schedule of Assessments.

The ECG parameters (heart rate, PR interval, QRS interval, QT interval, and corrected QT [QTc] interval) at each time recorded, as well as the change from screening will be listed and summarized. These parameters will be determined electronically by the ECG machine at

Memorial Sloan Kettering Cancer Center
[name]
[name]

the clinical site. The QT interval will be corrected by both the Bazett and Fredericia methods as follows:

- Bazett: $QTcB = QT/(RR)^{1/2}$
- Fredericia: $QTcF = QT/(RR)^{1/3}$

The overall ECG assessment will be reported as “Normal” or “Abnormal” with respect to relevant abnormalities by the investigator. A shift table comparing the ECG assessment over the study drug administration period to screening will be presented.

The QTc data obtained by using the Bazett and Frederician corrections will be categorized separately into the following classifications and summarized by time after study drug dosing:

- QTc interval >450 msec and ≤ 480 msec
- QTc interval >480 msec and ≤ 500 msec
- QTc interval >500 msec

The change of the QTc values obtained by using the Bazett’s and Frederica’s correction will also be categorized separately as follows:

- QTc interval increases from baseline by >30 msec and ≤ 60 msec
- QTc interval increases from baseline by >60 msec

The calculated QTc average of the 3 ECGs must be <480 msec for eligibility.

The average of triplicate 12-lead ECG results will be summarized by treatment at each time point using descriptive statistics (number of subjects, mean, SD, median, minimum, and maximum).

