11.10 Post-study Follow-up

The post-study follow-up will include the end of treatment (EoT) visit, the safety follow-up visit, and the long-term follow-up. The purpose of these additional visits post follow-up is for safety. No additional biomarkers will be collected for study purposes after the EoT visit.

An End of Treatment (EoT) visit will be performed within 7-14 days after the administration of the last dose of the last study drug.

Memorial Sloan Kettering Cancer Center
[name]
[name]

The safety follow-up (FU) visit will be performed 30 days after the last dose of the study drug (except for subjects who died, withdrew consent, and objected to further data collection or were lost to follow up). The safety FU assessment can be done via the clinic visit (recommended) or via a phone call (if subject cannot attend the clinic visit or has started a new anti-cancer treatment). The investigator may order unscheduled FU visits after the 30-day safety FU visit if the adverse events ongoing at the safety FU are deemed to be clinically significant and related to the study drug(s).

The long-term follow-up visits will be performed via clinic visit or phone call every 3 months for 12 months after the last dose of the study drug (except for subjects who died, withdrew consent and objected to further data collection or were lost to follow up).

Memorial Sloan Kettering Cancer Center
[name]
[name]

Schedule of Assessments (SOA) Table 3

Study Procedures	Treatment Visits (+/- 3 day window)						Follow-up		
	Screening (within 28 days of C1D1)	Cycle 1 ¹⁴		Cycle 2		Cycle 3+		EOT +/- 3 days	Safety Follow- up +/- 3 days
		Day 1	Day 15	Day 1	Day 15	Day 1	7-14 days of last dose	30 days of last dose	Q3 months for 1 year after last dose
Informed Consent	Within 45 days								
Demographics	X								
Complete medical history	X								
Pre-Treatment Core Biopsy or Archival tissue	X ⁴								
Genomic molecular profile (historic report)	X								
Abbreviated medical history		X							
Concomitant medications	X	X	X	X	X	X	X	X	
Toxicities	X	X	X	X	X	X	X	X	X ¹⁴
Physical exam	X	X		X		X		X	
ECOG performance status	X	X	X	X	X	X	X	X	
Vital signs ¹	X	X	X	X	X	X	X	X	
12-lead ECG, in triplicate ¹²	X	X		X		Cycle 5 and every odd Cycle thereafter	X		
NYHA classification	X	X		X		Cycle 5 and every odd Cycle thereafter	X		
Hematology ¹⁵	X	X	X	X	X	X	X	X	
Chemistry ¹⁵	X	X	X	X	X	X	X	X	
Urinalysis (Dipstick) ¹⁵	X	X	X	X	X	X			

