14.7 Pharmacokinetic Analyses

PK parameters for mirdametinib and PD-0315209 will be calculated using non-compartmental analysis with appropriate software such as Phoenix WinNonlin (Version 8.1 or higher, Certara, Inc.). Only plasma concentrations greater than or equal to the validated lower limit of quantitation (LLQ) will be used in the PK analyses. Actual blood sampling times will be used in all PK analyses. Per-protocol times will be used to calculate mean plasma concentrations for graphical displays.

The following PK parameters will be determined as appropriate:

C_{\max}	Maximum concentration, determined directly from individual concentration-time data (Cycle 1, Day 1 only)
$C_{\max, ss}$	Maximum concentration at steady-state, determined directly from individual concentration-time data (Cycle 1, Day 15 only)
$C_{\text{trough}, ss}$	Minimum concentration at steady-state, determined directly from individual concentration-time data (Cycle 1, Day 15 and Cycle 2, Day 1 only)
T_{\max}	Time to reach maximum concentration, determined directly from individual concentration-time data.
AUC_{last}	Area under the concentration-time curve from time-zero to the time of the last quantifiable concentration; calculated using the linear-up/log-down trapezoidal rule (Cycle 1, Day 1 only)
$AUC_{\text{last}, ss}$	Area under the concentration-time curve from time-zero to the time of the last quantifiable concentration at steady-state; calculated using the linear-up/log-down trapezoidal rule (Cycle 1, Day 15 only)

Additional PK parameters may be calculated if data allows. Population PK modeling may be performed on the mirdametinib concentration-time data collected from this study to quantitatively describe the PK, explore the PK variability, and identify any covariate effects such as demographic, intrinsic or extrinsic factors, or co-medication on the PK. The exposure-response relationship between measures of mirdametinib exposure and measures of efficacy, including, but not limited to, ORR, PFS, and DOR may also be explored. The relationship between mirdametinib exposure and key safety variables, including EKG, may be explored. In addition, tumor biopsy biomarkers may be explored in the exposure / response analyses.

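### The second 4-hour post-dose ECG sits on C2D1, after the DLT window and without a paired concentration, while C1D15, the steady-state PK day, has no ECG

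*Combined protocol and SAP*

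**What the plan says.** **ECG schedule.** The row "12-lead ECG, in triplicate" in Table 3 (Section 11.10) is marked at screening, C1D1, C2D1, Cycle 5 and odd cycles after that, and end of treatment. The C1D15 cell is blank. Footnote 12 states "The triplicate ECG will be done pre-dose and at 4 hours post-dose on C1D1 and C2D1", and then "All other triplicate ECGs will be obtained pre-dose".

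**PK schedule.** Footnote 6 sets sampling at "Day 1 and Day 15 of Cycle 1: pre-dose and at 0.5h, 1.0h, 2.0h and 4.0h after the mirdametinib dose", and for the next cycle only "Day 1 of Cycle 2: pre-dose". Footnote 5 has the morning dose given in clinic on C1D1, C1D15 and C2D1.

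**Order and use.** Section 11.4 says "ECG monitoring should be performed prior to PK blood draws". Section 14.7 derives the steady-state maximum concentration and AUC from C1D15, and adds: "The relationship between mirdametinib exposure and key safety variables, including EKG, may be explored". Section 14.4 plans descriptive and categorical ECG summaries. Table 1 lists abnormal ECGs within the primary safety endpoint of both arms.

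**DLT window.** Section 15.3 counts DLTs over Days 1 to 28 of Cycle 1. Section 4.2 sets 28-day cycles.

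**Accumulation.** Section 3.1 gives AUC accumulation ratios of 1.3 to 1.9 for mirdametinib after 21 days of BID dosing, and says of the active metabolite: "Accumulation of the primary metabolite, PD-0315209, was higher at approximately 3-fold".

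**The concern.** The ECG and PK schedules diverge at the visit where they would be most useful together. On C1D15 the patient is dosed in clinic, stays 4 h and gives five samples at steady state, and no ECG is recorded. On C2D1 a 4 h ECG is recorded and no concentration goes with it.

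Two things are at stake. First, the 3+3 decisions in both arms turn on Cycle 1 DLTs, and Arm 2 escalates to 8 mg BID on that basis. The only on-drug ECG scheduled in the DLT window follows a single dose, so a QTc effect that develops with accumulation is not scheduled to be seen there. Section 4.2 itself acknowledges a wide gap in safety information for continuous dosing in this range. Second, if exposure is related to ECG findings, there is no measured post-dose pair at steady state.

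**Working it through.** The plan gives no figure on this point to reproduce. The check compares the two schedules and then asks what exposure each ECG represents.

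**1. Matching the times, C1D1 to C2D1**

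| Visit (nominal day) | ECG | PK | Matched times |
|---|---|---|---|
| C1D1 (Day 1) | 0, 4 h | 0, 0.5, 1, 2, 4 h | 0 and 4 h |
| C1D15 (Day 15) | none | 0, 0.5, 1, 2, 4 h | none |
| C2D1 (Day 29) | 0, 4 h | 0 h | 0 h |

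(0 = pre-dose.) There are three matched times: C1D1 pre-dose, when no drug is on board; C1D1 at 4 h, after the first dose; and C2D1 pre-dose, a trough on continuous dosing. The C2D1 4 h ECG has no concentration, and all five C1D15 samples have no ECG. There are no matched post-dose pairs at steady state.

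**2. Position against the DLT window**

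C2D1 = 28 + 1 = Day 29, and the window closes on Day 28. Both scheduled ECGs inside the window are on Day 1, one of them before any drug.

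**3. Is C1D15 at steady state?**

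Inputs are the Section 3.1 terminal half-lives: 22 to 30 h for mirdametinib and 30 to 40 h for the metabolite. Fraction of steady state after t hours = 1 − 0.5^(t / half-life). From the first dose to C1D15, t = 14 × 24 = 336 h.

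- Slowest case, metabolite at 40 h: 1 − 0.5^(336/40) = 0.997.
- Mirdametinib at 30 h: 1 − 0.5^(336/30) = 0.9996.

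So exposure is at least 99.7% of steady state, in agreement with Section 14.7.

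**4. Exposure represented by the C1D1 4 h ECG**

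First-dose share of steady state = 1 / R, where R is the accumulation ratio.

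- Mirdametinib: 1/1.9 = 0.53 to 1/1.3 = 0.77.
- Metabolite: 1/3 = 0.33.

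This gives very roughly one-third to three-quarters. For mirdametinib, R is a ratio of AUC over the dosing interval; for the metabolite, Section 3.1 does not state its basis. Applying 1/R at a single 4 h time is an assumption, because the documents give no 4 h concentrations.

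**5. Intermittent levels (-1INT and -2INT)**

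With three weeks on and one week off, C2D1 follows 7 × 24 = 168 h without drug. Fraction remaining = 0.5^(168 / half-life).

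- Mirdametinib: 0.5^(168/22) = 0.5% to 0.5^(168/30) = 2.1%.
- Metabolite: 0.5^(168/30) = 2.1% to 0.5^(168/40) = 5.4%.

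The C2D1 4 h ECG at these levels is again close to a first-dose reading, so no scheduled post-dose ECG is at steady state. C1D15 falls within the dosing weeks on every schedule.

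**6. After the change**

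ECG times become C1D1 0 and 4 h, C1D15 4 h, and C2D1 0 h: four triplicates, as now. All four have a PK sample, so matched times rise from 3 to 4. Matched steady-state post-dose pairs rise from 0 to 1, inside the DLT window.

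**The case against.** A reader might infer that a QTc effect at steady state cannot enter the 3+3 decision. The documents do not support that. Section 4.2 bases the decisions on DLTs and the overall safety profile, with review of all available safety and PK data. A patient without a DLT becomes evaluable only on completing Cycle 1, so the review falls near C2D1 in any case. The ±3-day window in Section 11.2 allows C2D1 on Days 26 to 32. Section 15.3 permits discretionary DLTs, and unscheduled ECGs remain possible. What stands is narrower: no steady-state ECG is scheduled within the window, and an abnormality first seen on Day 29 is not a DLT under the Day 1 to 28 definition.

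Other strong readings also go too far:

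- **C2D1 has no PK match.** Its pre-dose ECG is matched; only the 4 h ECG is not.
- **Section 11.4 requires a PK sample with every ECG.** It sets the order of procedures and no more.
- **A planned exposure-ECG analysis is defeated.** Section 14.7 makes that analysis optional. It also allows population PK modelling, which on continuous dosing might predict the missing C2D1 concentration from the C1D15 profile and the C2D1 trough.
- **The primary endpoint is not covered.** Table 1 does not limit ECG findings to Cycle 1, so later ECGs count.

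On weight, Section 15.6 does not list QT prolongation among expected reactions. Section 3.4 places the cardiac events mainly at 10 mg BID and above, higher than any planned dose. Table 4 has QTcF rules with repeat triplicates. The intermittent levels open only if higher levels fail. These points limit the importance of the gap. They do not explain why steady-state PK and the second post-dose ECG fall on different days.

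**Conclusion.** The point holds as a design weakness. Nothing in the documents is contradictory. The only scheduled on-drug ECG in Cycle 1 is 4 h after the first dose, the other 4 h ECG is on nominal Day 29 without a concentration, and the steady-state PK day has no ECG. At the two intermittent levels, no scheduled post-dose ECG is at steady state.

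The schedule facts rest on no assumptions beyond nominal visit days. The steady-state and washout figures assume first-order elimination at the stated half-lives. The one-third to three-quarters range is a rough guide, applies only to the C1D1 4 h ECG, and depends on the accumulation ratios holding at that time point. The consequence is a missed opportunity within the DLT window and in the optional exposure-ECG exploration. It does not block the safety review.

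**What to change.** In footnote 12 and the ECG row of Table 3, move the 4 h post-dose triplicate from C2D1 to C1D15, taken just before the 4 h PK draw already scheduled there. Keep the C2D1 pre-dose triplicate.

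The change is schedule wording. C1D15 already has in-clinic dosing and a 4 h stay for PK. The ECG would no longer require a 4 h stay on C2D1, where PK is pre-dose only. Change from baseline needs no C1D15 pre-dose ECG, because Section 11.4 summarises change from screening.

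The cost is the loss of the C2D1 post-dose reading, which in Arm 1 is the one taken after the Day 15 fulvestrant dose. Keeping the C2D1 pre-dose ECG limits that loss. It also leaves the interval to the next scheduled ECG, at C5D1 (4 × 28 + 1 = Day 113), at 113 − 29 = 84 days. Moving both C2D1 ECGs would lengthen it to 113 − 15 = 98 days, which is why only the post-dose one should move.
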